### **Study Overview**

Two test meals will include the same cut and quality of pasture-fed New Zealand beef or grain-fed New Zealand beef of well-defined provenance, which has been specifically slaughtered, packaged and stored for this trial. The third test meal will be lamb meat that will be sourced from New Zealand as a representative sample. The fourth test meal will be a commercial plant-based meat alternative that best resembles in terms of appearance and macronutrient profiles.

Meals will include a 220 g raw serving of beef or lamb (approximately 160 g cooked), which is in line with the World Cancer Research Fund / International Agency for Research on Cancer recommendation on red meat consumption, which suggests limiting the weekly red meat consumption to 350-500 g cooked. A minimum quantity of 100 grams cooked meat is required to ensure adequate fat intake to allow assessment of post-meal lipid dynamics [19]. The test meals will be provided in the morning after an overnight fast. The meals will look identical in appearance and participants will not be told which meal they have received.

Saliva samples will be collected at one time prior to meal consumption (baseline). These samples will be sent for subsequent analysis at the Nutrigenomix Inc laboratory. The test analyses variations in 70 genes that impact nutrient metabolism, eating habits, weight management and body composition, food intolerances and physical activity. The accuracy of the genetic test results are between 99.7 – 100%.

Blood samples will be collected immediately prior to (baseline) and 60, 120, 180 and 240 minutes following the meal for serum and EDTA plasma. Bloods will be taken in the phlebotomy room in the research facility, by a phlebotomist using via an indwelling catheter. Blood samples will be processed and frozen at -80°C for subsequent analysis.

During this time of each visit, participants will remain in the research unit. Appetite, digestive comfort and palatability scores will be self-reported using manual questionnaires.

The SPIRIT reporting guidelines for the accurate documentation of clinical trial protocols has been followed [16]. See Table 1 for trial schedule.

**Table 2.** SPIRIT Chart. Schedule of enrolment, interventions, and assessments

TIMEPOINT	STUDY PERIOD									
	Enrolment	Allocation			Post-allocation					Close-out
	-t1	0	tpre	t0	t30	t60	t120	t180	t240	+t1
ENROLMENT:										
Eligibility screen	X									
Informed consent	X									
Allocation		X								
INTERVENTION MEALS:										
Grain-fed Beef		Random order		X						
Grass-fed Beef		Random order		X						
Lamb		Random order		X						
Meat Alternative		Random order		X						
ASSESSMENTS:										
Amino acids			X			X	X	X	X	
Neurotransmitters			X			X	X	X	X	
Inflammatory Markers			X			X	X	X	X	
Chylomicron fatty acids			X			X	X	X	X	
Chylomicron Lipidomics			X						X	
Glucose/ Insulin			X			X	X	X	X	
Vitamins (ADEK)			X			X	X		X	
Vitamins (Bs)			X			X	X		X	
Haemoglobin/ Minerals			X			X	X	X	X	

Saliva genetic markers			X							
Questionnaire-Fullness			X	X	X	X	X	X	X	
Questionnaire-Digestive Symptoms			X	X	X	X	X	X	X	
Questionnaire-Palatability					X					
Questionnaire-Participant Insight										X

## Intervention

All meals will be prepared according to standardised recipes by the Research Dietitians and served at the test kitchen site in The University of Auckland Clinical Research Centre. The meat will be minced to ensure homogeneity between participants. All non-meat food items will be purchased at a local supermarket. The test diets will be protein and fat matched, and the meals will be balanced for energy, carbohydrate and fibre. A panel of meat scientists, a nutritionist and research dietitian reviewed available options to choose the plant-based meat analogue. Their criteria included 1) nutrition should approximate beef, 2) appearance should approximate beef, and 3) readily available in the retail space. Nutrient content data for the beef mince was based on New Zealand composition tables, and for the analogue was taken from the NIP.

All participants will be fasted for 10 hours prior to consuming the test meal. All test meals will be given in the morning, as postprandial lipid responses are greatest at this time [17].

## Outcomes (Primary and Secondary)

Following the consumption of a single meal:

Primary outcome variable

- Change in LCPUFA (18:2 n-6, 18:3 n-3, 20:4 n-6, 20:5 n-3, 22:5 n-3, 22:6 n-3) concentrations in the chylomicron fraction over 4 hours. Difference in the change between pasture-, grain-beef, lamb and plant-based alternative meat meals.

Secondary outcome variables

- Differences in other fatty acid (14:0, 16:0, 16:1 n-7, 18:0, 18:1 n-9, others) concentrations in the chylomicron fraction over 4 hours.
- Differences in the plasma amino acid (isoleucine, leucine, valine, histidine, lysine, methionine, phenylalanine, threonine, alanine, arginine, asparagine, aspartic acid, glutamic acid, glutamine, glycine, proline, serine, tyrosine, 3-methylhistidine, citrulline, hydroxyproline, ornithine, taurine, others) concentrations over the 4 hours.
- Differences in plasma neurotransmitter concentrations (phenylethyl amine, 3,4-dihydroxyphenylalanine, dopamine, 3-methoxytyramine, 3,4-dihydroxyphenylacetic

acid, homovanillic acid, norepinephrine, 3,4-dihydroxyphenylglycol, 3-methoxy-4-hydroxyphenylglycol, normetanephrine, epinephrine, metanephrine, vanillylmandelic acid, tryptophan, kynurenine, 5-hydroxytryptophan, serotonin, 5-hydroxyindoleacetic acid, alpha-aminobutyric acid, gamma-aminobutyric acid).

- Differences in minerals and haemoglobin concentrations.
- Change in inflammatory markers (TNF $\alpha$ , IL-1, IL-6, IL-8, IL-10, IL-13, hs CRP).
- Digestive differences based on genetic profile.
- Differences in subjective experience to the meal including fullness, satisfaction, gastrointestinal comfort scores among pasture-, grain- and plant-based alternative meat meals.
- Qualitative differences in the participant's opinions regarding future red meat consumption ("Participant insights").
- Adverse events, count score differences between meals.

## Measurements

### *Blood and Plasma Analyses*

Serum samples will be kept at room temperature for 15 minutes prior to centrifugation and storage of supernatant at -80°C until analysis. An aliquot of plasma will be maintained at 4°C for the chylomicron-rich fraction (CMRF) separation to occur within 6 h, with the remaining stored at -80°C until analysis.

Fatty acid composition of the CMRF will be analysed by the fatty acid methyl esters (FAME) assay as previously described [21] and by lipidomics, as previously described [22].

Plasma amino acid analysis will be conducted using ultra performance liquid chromatography (UPLC) according to previously published methods [23, 24]. The four test meals will also be analysed for their final amino acid content.

The analysis of plasma B-vitamins including thiamine; riboflavin and its vitamers FMN; the B3 vitamers: nicotinic acid, nicotinamide and nicotinuric acid, and pantothenic acid; and the B6 vitamers pyridoxal, pyridoxamine, PLP, and 4-pyridoxic acid will be performed by ultra-high-performance liquid chromatography-tandem mass spectrometry (UHPLC-MS/MS) using a method published previously [25], within the Liggins Institute, New Zealand.

Blood samples will be prepared under the fat-soluble vitamin procedure and analysed using the fat-soluble vitamin LC-MS method [26]. Samples will be analysed by AgResearch, New Zealand.

Neurotransmitters will be assessed by mass spectroscopy. The methodology utilises a MS-probe and stable isotope coding LC MS method developed by AgResearch and has been optimised for plasma samples. The protocol aligns with published protocol data [26].

Minerals will be assessed using the ICP-MS at Analytica Laboratories, Hamilton, New Zealand as per the following protocol, optimised for plasma samples. The samples will be analysed on an Agilent 7700 ICP-MS (Agilent Technologies, Wilmington, DE, USA) fitted with an ASX500 autosampler (CETAC Technologies, Omaha, NE, USA) and MiraMist nebulizer (Burgener Research, Mississauga, ON, Canada). The argon consumption in the torch will be 20 L/min and the collision cell will be operated with 4 mL/min helium. All consumables will

be supplied by Agilent Technologies. Eighteen elemental species [sodium (Na), magnesium (Mg), aluminium (Al), K, calcium (Ca), vanadium (V), chromium (Cr), manganese (Mn), Fe, cobalt (Co), nickel (Ni), copper (Cu), zinc (Zn), selenium (Se), bromine (Br), silver (Ag), antimony (Sb) and barium (Ba)] will be analysed. For the analysis, plasma samples will be diluted 25-fold with 2.8% ammonia, 10% isopropanol, 0.2% Triton X solution and 0.1% EDTA. Following dilution, an internal standard containing scandium (Sc), germanium (Ge), yttrium (Y), rhodium (Rh), terbium (Tb) and iridium (Ir) will be added. A standard curve will be generated using five concentrations (0.1, 1, 10, 100 and 1000 µg/L), prepared from Agilent Multi-element Calibration Standard 2A (Agilent Technologies, Santa Clara, CA, USA). A separate calibrator for bromine (Br) will be prepared from 1000 mg/L KBr (o2si Smart Solutions, Charleston, SC, USA). Na, K, Ni and Sb will not be calibrated and these results can therefore only be expressed as arbitrary units (AU). Blanks and certified reference serum material (Seronorm™ Trace Elements Serum L-1, SERO, Billingstad, Norway) will be used throughout the analysis to maintain precision and accuracy. Reference material will be prepared according to the manufacturer's instructions and was diluted in the same manner as the plasma samples (i.e., 1 in 25 with ammonia diluent, as described above), and the Seronorm™ values will be assigned in accordance with the Essential Requirements (Annex 1 of the IVD Directive 98/79/EC) and the ISO17511 International standard. Polyatomic interferences were overcome because the Agilent 7700 uses the Octopole Reaction System (ORS) with Helium as the collision gas. Element isotopes selected were those with the least interference. The Agilent Multielement standard 2A is traceable to the NIST Standard Reference Material and was produced using ISO9001 quality procedures.

Plasma inflammatory markers will be analysed in duplicate using the Invitrogen's Inflammation 20-Plex Human ProcartaPlex™ Panel (catalogue number: EPX200-12185-901). Briefly, 25 µL of plasma and internal controls will be incubated with magnetic beads prior to a series of wash steps. 25 µL of detection antibody will be added and incubated for 30 min before 50 µL of Streptavidin-PE was added. The 96-well plate will then analysed using BioPlex® 200 system (BioRad) with inflammatory markers being measured in pg mL.

Plasma glucose and cholesterol (total, LDL, HDL) and triglyceride will be measured using a Roche Cobas c311 by enzymatic colorimetric assay and insulin will be measured by an electrochemiluminescence immunoassay.

### *Saliva analyses*

Saliva samples will be collected in an Oragene ON-500 saliva collection kit and sent to the Nutrigenomix laboratory centre at University of Toronto, Canada. The iPLEX Gold assay with mass spectrometry-based detection on the Sequenom MassARRAY platform (Agena Bioscience, San Diego, CA, USA) will be used for all genotyping. The test will analyse variations in 70 genes related to nutrient metabolism, eating habit and food intolerances.

### **Subjective Analyses**

Satisfaction and gastrointestinal comfort scores will be analysed using a 10 cm visual analogue scale, previously validated for use in single meal investigations [27]. Satisfaction scores will be completed by the participants upon arrival, once immediately prior to meal ingestion (two baseline assessments to account for individual variation), immediately following ingestion, and then timed with blood sampling for 4 hours.

Gastrointestinal comfort scores will be analysed by a questionnaire consisting of a series of visual analogue scales using intensity anchors (“no symptom”, “the most severe symptom imaginable”). Gastrointestinal comfort scores questionnaires will be completed by the participants upon arrival, immediately prior to meal ingestion (two baseline assessments to account for individual variation), immediately following ingestion of the meal, and then timed with blood sampling for 4 hours.

Participant insights will be assessed via a closed and open-ended questionnaire to ask the participant to guess which meat-type they were provided the day prior and the degree to which they are likely to consume red meat in the future, with reasoning. The survey will also specifically ask for any adverse reactions to the test meal. The participants will be asked to complete a survey the day following the final test meal trial, a link to the Qualtrics (SAP, Utah, US) survey will be emailed.

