### **Methods**

A cohort of healthy, young (20-34 years old) male participants will consume a single meal on four occasions in a treatment-crossover, blinded investigation. Each instance will be followed by four hours of repeated venous blood collection to assess the digestive and metabolic effects of the meal. The four meals include a popular commercial meat analogue comprising pea, bean and rice extracts plus plant fats and cellulose, or a mince from pasture-raised or grain-fed beef or grass-raised lamb. Blood plasma samples of the participants will be measured for changes in chylomicron fatty acid distribution, amino acid profile, neurotransmitter proteins, minerals, inflammatory markers and biomarkers of general health.

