## **METHODS/DESIGN**

### **Study Setting**

The trial will be conducted at the University of Auckland Clinical Research Centre. The study is a randomised crossover trial to capture biological difference in postprandial nutrient dynamics. Research subjects will act as their own controls and will consume each meal on a separate occasion in random order. The study compares exemplars of pasture-fed New Zealand beef, grain-finished New Zealand beef, New Zealand lamb and a plant-based meat analogue. The pasture-fed beef was obtained from Angus Steers that had been fed exclusively on pastures (ryegrass and white clover mix) whereas the grain-finished beef was Angus steers that had been finished for an average of 122 days on a maize silage, barley wheat and straw ration. Marble score (3-4/9 on the Australian Grading System) [15] and pH (average 5.5) of the meat were consistent between production systems. The lamb will be sourced from New Zealand. The meat analogue has been selected from commercial varieties on the basis of its macronutrient profile (protein and fat) and appearance to best match that of meat.

The digestion and metabolism of key nutrients will be measured immediately after the ingestion of a single meal. This experimental setting will also be used to examine some subjective qualities of the meal experience, such as satisfaction score (i.e., liking, satisfaction, enjoyment, satiety, appetite) and gastrointestinal score (i.e., comfort, fullness, bloating, rumbling, flatulence, faecal urgency, diarrhoea).

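### The gastrointestinal score lists flatulence, faecal urgency and diarrhoea but stops at 240 minutes, and the only later question on symptoms is sent once, after the fourth meal.

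*Protocol*

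**What the plan says.** Under Study Setting, the Protocol defines a "gastrointestinal score (i.e., comfort, fullness, bloating, rumbling, flatulence, faecal urgency, diarrhoea". Under Outcomes (Primary and Secondary), one secondary outcome is "Differences in subjective experience to the meal including fullness, satisfaction, gastrointestinal comfort scores" compared among meals.

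The Subjective Analyses section sets the timing. The questionnaire is completed on arrival, immediately before the meal, "immediately following ingestion of the meal, and then timed with blood sampling for 4 hours". The Study Overview fixes the blood times: "Blood samples will be collected immediately prior to (baseline) and 60, 120, 180 and 240 minutes following the meal". In Table 2, the row "Questionnaire-Digestive Symptoms" has its last mark at 240 minutes, and its close-out cell is empty.

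One later instrument exists, the participant insights survey. On content, Subjective Analyses says: "The survey will also specifically ask for any adverse reactions to the test meal". On timing, it says: "The participants will be asked to complete a survey the day following the final test meal trial". Table 2 marks this survey at close-out only. The Adverse events section takes all study-related adverse events from a survey after the meal, and the outcome list includes adverse event counts compared between meals.

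**The concern.** The symptom window follows the blood-sampling schedule, and the Protocol gives no symptom-based reason for ending at 4 hours. That suits the items about comfort and fullness during the visit. It suits the lower-bowel items less well, because some of those symptoms may plausibly begin after the participant has gone home. If so, they never enter the score, and a true difference between meals on those items shrinks towards zero.

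The direction matters for interpretation. A finding of similar digestive comfort could partly reflect when scoring stopped. The Trial Design section adopts a non-inferiority framework. The Protocol does not tie that framework to the gastrointestinal score, but wherever similarity is the conclusion, attenuation works in its favour.

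The adverse event outcome might have filled the gap, but its single collection point comes after the last of four meals.

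**Working it through.** The Protocol gives no sample size, variance, margin or power for the gastrointestinal score, so there is no stated figure to reproduce. The check is mainly a comparison of sections.

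**1. Scored window.** Text and schedule agree on seven assessments: two before the meal, one just after it, and four at 60, 120, 180 and 240 minutes. Table 2 has seven marks in the digestive-symptom row, the last at 240 minutes. Scored assessments after 240 minutes: none, for any meal.

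**2. Items affected.** The Study Setting list has seven items. Flatulence, faecal urgency and diarrhoea are three of them. The other four (comfort, fullness, bloating, rumbling) are not the subject of this point.

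**3. Coverage by the later survey.**
- Completers: 29 (Sample size calculation). Meals per participant: 4.
- Participant-meals: 29 × 4 = 116.
- Participant-meals directly followed by the survey: 29 × 1 = 29, and 29/116 = 25%.
- Participant-meals left to recall: 116 − 29 = 87.
- Because meal order is random, the final meal differs between participants. With balanced order, about 29/4 ≈ 7 next-day answers would refer to each meal. Each participant gives a next-day answer for one meal only, so the within-participant comparison that the crossover provides is not available for this information.

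**4. Recall interval.** Meals are one week to one month apart (Randomisation and Blinding). Counted back from the final meal, the third was at least 1 week earlier, the second at least 2 weeks and the first at least 3 weeks. If every gap is at its maximum, these become 1, 2 and 3 months. The survey comes one day later still.

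**5. Consistency of the survey's description.** Subjective Analyses asks participants to guess the meal they ate on the previous day, which fits a survey after each meal, yet the same paragraph sends it only after the last one. The Adverse events section relies on a post-meal survey for all events, and the outcome list needs counts for each meal. These three statements do not fit together as written.

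**6. Illustration of attenuation (assumptions only).** Let *f* be the share of a between-meal difference that shows within 4 hours, and *d* the standardised paired difference if everything were captured. Assume the spread does not change with the window. Approximate two-sided 5% power is Φ(*d* × *f* × √29 − 1.96). With *d* = 0.54, *d* × √29 = 0.54 × 5.385 = 2.908.

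| *f* | *d* × *f* × √29 − 1.96 | power |
|---|---|---|
| 1.00 | 0.948 | 83% |
| 0.75 | 0.221 | 59% |
| 0.50 | −0.506 | 31% |
| 0.25 | −1.233 | 11% |

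Neither *f* nor *d* is in the documents. The table shows how the loss would scale, not how large it is.

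**The case against.** The strongest reply is that the 4-hour window is the stated scope and is used consistently. The trial is described as acute and single-meal, the subjective measures are an addition to that setting, and no section promises symptom data over a day or makes an explicit tolerability claim. This stands: the window contradicts nothing. What remains is a design choice that leaves three listed items only partly observed.

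Several stronger readings are tempting, and the documents do not support them.

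- **The meals will look equally tolerated by construction, with the late items near zero for every meal.** The same window applies to all meals, early symptoms can differ, and four of the seven items are untouched. The Protocol gives no transit times.
- **A calculable share of the difference is lost.** Assuming that 50% to 90% of symptoms start after 4 hours yields an observable share of 50% to 10%, but that only restates the assumption. Setting 4 hours against 24 hours (17%) uses a denominator the Protocol does not give.
- **The analogue must be the meal that differs.** It is described as "a popular commercial meat analogue comprising pea, bean and rice extracts plus plant fats and cellulose", which makes the expectation plausible. However, the Intervention section balances the meals for carbohydrate and fibre. The point does not depend on which meal differs.
- **Late symptoms are missed altogether.** A troublesome reaction can be reported in the survey. That safeguard is real but weak: it comes once, it is described without the symptom scales, and it relies on recall for three of the four meals.

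It is also fair that this concerns three items within one secondary outcome. The primary outcome is unaffected.

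**Conclusion.** The point holds as a cheap improvement. The gastrointestinal score measures symptoms to 4 hours only. Lower-bowel symptoms that begin later are unscored for all four meals, which may attenuate a between-meal difference on three of the seven items. The size of that loss is unknown, because it depends on the share of symptoms starting after 4 hours.

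The firmer part is documentary. The only later capture directly follows 29 of 116 participant-meals (25%, assuming 29 completers and the survey timing as written), while the Protocol plans adverse event counts compared between all meals. A null gastrointestinal result would support similar symptoms up to 4 hours and no more.

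**What to change.** In Subjective Analyses and Table 2, add one short online questionnaire on the evening of, or the morning after, each of the four meals. It should carry the same 10 cm gastrointestinal scales plus the adverse-reaction question, and cover the time since leaving the unit. Keep the 0–4 hour score exactly as planned and report the late items separately. State the survey timing in the same way in Subjective Analyses, Table 2 and the Adverse events section, so that adverse event counts can be attributed to each meal.

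The cost is four short surveys per participant (116 for 29 completers), one more column in Table 2 and a protocol amendment. The online survey tool and text messages are already planned, but for one final survey and for attendance reminders, so their use would have to be extended. Food eaten after leaving the unit is uncontrolled and adds noise. Random meal order keeps that noise from favouring any meal, though it lowers precision. The change has to be in place before visits begin, because prompt late reports cannot be recovered afterwards.

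If the questionnaire is not added, limit any conclusion of no gastrointestinal difference to symptoms up to 4 hours, and still reconcile the survey timing with the between-meal adverse event comparison.

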## **DISCUSSION**

### **Adverse events**

All study-related adverse events will be requested in the post meal survey and will be listed in the final trial report. Serious adverse events will be reported to the Health and Disability Ethics Committee.

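### Adverse events have three different scopes, and the participant must judge cause before an event reaches the between-meal count

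*Protocol*

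**What the plan says.** Three sections of the Protocol define what is collected.

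- **Outcomes (Primary and Secondary)**, last secondary outcome: "Adverse events, count score differences between meals". No limit by cause is given.
- **Adverse events**: "All study-related adverse events will be requested in the post meal survey and will be listed in the final trial report". A separate sentence sends serious events to the ethics committee and does not tie them to the survey.
- **Subjective Analyses**, in the paragraph on participant insights: "The survey will also specifically ask for any adverse reactions to the test meal". The same survey asks the participant to "guess which meat-type they were provided the day prior" and how likely he is to eat red meat in future.

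Under Study Overview, blood is taken "by a phlebotomist using via an indwelling catheter" at baseline and at 60, 120, 180 and 240 minutes. The same section adds: "During this time of each visit, participants will remain in the research unit". It does not say that staff record adverse events. The schedule (Table 2) has no adverse-event row. The survey appears there as "Questionnaire-Participant Insight", marked once, at close-out.

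**The concern.** Adverse events, study-related adverse events and reactions to a test meal are nested sets, and each is smaller than the one before. The only description of the survey's content uses the smallest set, while the reporting promise and the outcome use the larger two. Two things are at stake.

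1. **Completeness of the safety list.** A bruise, a sore catheter site or a faint during sampling is study-related but is not a reaction to the meal. A man who answers the question as described has no reason to mention it.
2. **Validity of the between-meal count.** If a symptom is reported only when the participant attributes it to the meal or to the study, the count depends partly on what he believes he ate and what he thinks of that food. The survey prompts exactly that belief by asking for a guess.

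An analysis plan cannot repair either problem later, because an event that was never asked for cannot be recovered.

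**Working it through.** The documents give no figure on this point, so the check compares the passages.

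**Step 1. Which events does each section cover?**

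| Type of event | Outcomes list | Adverse events section | Survey item as described |
|---|---|---|---|
| Symptom attributed to the meal | yes | yes | yes |
| Catheter or blood-sampling event | yes | yes | not evidently |
| Event not attributed to the study | yes, on its plain words | no | no |

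The middle row is a direct mismatch between what is promised and what the survey is described as asking. The last row conflicts only with the outcomes list, since the Adverse events section is itself limited to study-related events.

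**Step 2. Is there another route?** For serious events there is a separate reporting sentence. For non-serious events only the survey is named. The gastrointestinal scales are completed on arrival, just before the meal, just after it, and then with the blood samples for 4 hours, whatever the participant thinks caused the symptom. They cover the symptoms listed under Study Setting (comfort, fullness, bloating, rumbling, flatulence, faecal urgency, diarrhoea). They do not cover catheter events, faintness, headache or anything after 4 hours, and the protocol does not say that their scores feed the adverse-event count.

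**Step 3. How much exposure to the procedure is there?** Inputs: 29 completers (Sample size calculation), 4 meals, 5 samples per visit (Study Overview).

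- Catheter visits: 29 × 4 = 116
- Blood samples: 116 × 5 = 580

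These figures measure opportunity, not events. The documents give no event rate.

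**Step 4. Who judges cause?** Under the Subjective Analyses wording, the participant decides whether the meal was responsible. Under the Adverse events wording, he decides whether the study was responsible. Either way he makes the judgement before anything is recorded. The concern about belief therefore does not depend on which wording reaches the questionnaire.

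**Step 5. Would missed catheter events distort the comparison of meals?** The catheter and sampling schedule is the same at every visit, whichever meal is served. Missed procedural events would shorten the list but should not favour any meal.

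**The case against.** The strongest reply is that the sections can be read together. The survey sentence is additive in form: it describes one specific item and does not exclude a broader one. The Adverse events section, which governs this topic, says that study-related events are requested in the survey. The questionnaire itself is not in the document. A reader might infer that the survey asks about meal reactions and nothing else, and that catheter events are therefore lost. The text supports neither inference. The loss is a risk if the described item is the full wording.

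Other parts of the reply also stand.

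- The outcome line is a short label and may not have been meant as a separate collection scope.
- Serious events have their own sentence, and digestive symptoms during the visit are scored regardless of attribution.
- Participants are blinded and the meals are meant to look identical, which limits the influence of belief. Blinding does not remove that influence if guesses are often right or are firmly held.
- The order of the survey items is not stated, so it cannot be said that the guess comes first.
- It is tempting to estimate how many events would be missed. That needs an event rate that the protocol does not give.

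The reply does not remove the mismatch in scope, the absence of any named second route for non-serious events, or the need for the participant to judge cause under both wordings.

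The timing of the survey, completed once after the final meal, is a separate question. This point does not depend on it.

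**Conclusion.** The point holds as an inconsistency in scope with two practical consequences. First, if the survey item is worded as Subjective Analyses describes, catheter and blood-sampling events that the Adverse events section undertakes to list may be missed across 116 catheter visits. That affects the completeness of the list, not the fairness of the comparison between meals. Second, on either wording the adverse-event count passes through the participant's own view of cause, so his belief about the meal could influence a declared secondary outcome. The direction and size of that influence cannot be derived from the documents, and they do not show that the count is in fact biased.

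The conclusion assumes that the survey is the only route for non-serious events, because the protocol names no other. If a visit record already captures them, the first consequence falls away and only the wording needs aligning. The primary outcome is not affected. This is a cheap improvement to a secondary outcome and to safety reporting.

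**What to change.** 1. Reconcile Outcomes, Subjective Analyses and Adverse events so that all three state one scope.
2. Word the survey item neutrally as to cause: ask for any symptom or health problem since the meal, whatever the participant thinks caused it.
3. Have the blood-collection staff, who are already present and blinded under Randomisation and Blinding, note catheter and sampling events on the form for each visit.
4. Count all events by meal for the secondary outcome, and list the study-related ones separately in the final report.

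The cost is one reworded survey item, one added line on the visit form and aligned text in three sections. The downside is a few more unrelated minor events to list.

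### Adverse events are to be compared between the four meals, but the only survey described as asking about them is timed once, after the last meal

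*Protocol*

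**What the plan says.** - **Protocol, Outcomes (Primary and Secondary):** the last secondary outcome is "Adverse events, count score differences between meals".
- **Protocol, Adverse events:** the collection route is given as "All study-related adverse events will be requested in the post meal survey". Serious events also have a reporting line: "Serious adverse events will be reported to the Health and Disability Ethics Committee".
- **Protocol, Subjective Analyses:** the participant-insight survey covers adverse reactions ("The survey will also specifically ask for any adverse reactions to the test meal"). Its timing is stated once: "The participants will be asked to complete a survey the day following the final test meal trial". The same survey asks men to "guess which meat-type they were provided the day prior".
- **Protocol, Study Overview, Table 2:** the row "Questionnaire-Participant Insight" carries one mark, in the Close-out column. There is no row for adverse events.
- **Protocol, Subjective Analyses, gastrointestinal comfort scores:** these are completed on arrival, just before eating, "immediately following ingestion of the meal, and then timed with blood sampling for 4 hours". They are a separate outcome and are not named as a source of adverse events.

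**The concern.** A comparison of adverse-event counts between meals needs each event tied to a meal, and so needs men to be asked about every meal. The only explicit timing rule places the question after the fourth meal. The reference to the previous day's meal, the singular test meal and the label post-meal survey all suggest a survey after each meal. Nothing in the Protocol settles which applies, and no section describes asking about adverse reactions after meals 1 to 3.

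Staff who follow the timing sentence could therefore fail to collect what the outcome requires, and no later analysis can recover reports that were never requested. Men may also withdraw at any time (Randomisation and Blinding). A survey sent only after the final meal would not reach a man who left earlier, including one who left because of a reaction.

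**Working it through.** The Protocol gives no figure on this point to reproduce. The check works out what each reading of the text delivers.

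**Inputs**
- 29 completers (Sample size calculation).
- 4 meals per man (Abstract, Methods).
- Consecutive meals one week to one month apart (Randomisation and Blinding). One month is taken as 31 days.
- Random order from a computer-generated sequence (same section); balance over positions is not stated.
- Assumption: every survey sent is answered.

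**Common quantities**
- Meal exposures: 29 × 4 = 116.
- Four meals form 6 pairs, so there are 6 × 29 = 174 possible within-man comparisons.

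**Reading 1: one survey, asking only about the last meal**
- Exposures with a report: 29 / 116 = 25%.
- Within-man pairs available: 0 of 174, because each man reports on one meal.
- Men per meal type: 29 / 4 = 7.25, about 7, if last positions are balanced. If order is simply random, the count is Binomial(29, 0.25), with 2.5% and 97.5% quantiles of 3 and 12.
- To show how little such a count says about a meal with no reported reactions, the exact two-sided 95% upper limit is 1 − 0.025^(1/n):

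| Men reporting on the meal | Upper limit |
|---|---|
| 3 | 71% |
| 7 | 41% |
| 12 | 26% |
| 29 (every man reports on the meal) | 12% |

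**Reading 2: one survey after meal 4, covering all four meals**

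All 116 exposures are covered. Recall in days is (number of gaps × 7) + 1 to (number of gaps × 31) + 1:

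| Meal | Gaps to meal 4 | Recall |
|---|---|---|
| 4 | 0 | 1 day |
| 3 | 1 | 8 to 32 days |
| 2 | 2 | 15 to 63 days |
| 1 | 3 | 22 to 94 days |

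The men are not told which meal was which (Study Overview), so they would have to place reactions by visit.

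**Reading 3: a survey after each meal**

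116 of 116 exposures are covered, with recall of about 1 day, and all 174 within-man pairs are available.

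**Under every reading**, gastrointestinal symptoms up to 4 hours are scored at all 116 exposures.

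**The case against.** The strongest reply is that a survey after each meal was plainly meant. The previous-day guess, the singular test meal, the post-meal label and the outcome itself all point that way, against the single word *final*. Table 2 does not decide it: it is one set of columns standing for four visits, so a mark under Close-out is consistent with a single survey but does not prove one. This may well be right. It still leaves the only explicit timing statement saying something else, and that sentence needs correcting.

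A second reply is that the survey named under Adverse events might be a separate instrument. No section says that it is the participant-insight survey. If it is separate, its timing is not given at all, and the need to state it remains.

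Third, the figures under Reading 1 require both that *final* is literal and that only the last meal is asked about. That is fair: they describe the worst of three readings and are not a prediction. The upper limits illustrate the loss of information; the Protocol does not plan to report them.

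Fourth, the stakes are modest. Healthy young men eat four single meals, gut symptoms are scored at each visit, and serious events go to the ethics committee. This stands and limits the point to non-serious reactions that are non-gastrointestinal or later than 4 hours. The symptom scales do not close that gap: they stop at 4 hours and are not named as an adverse-event source.

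**Conclusion.** The concern holds. The Protocol sets a between-meal adverse-event outcome and gives conflicting indications of when the men are asked. As literally timed, the survey leaves either 25% of exposures with a report and no within-man comparison, or recall of up to about 94 days for the first meal. If a survey after each meal was intended, the outcome is sound and the defect is one sentence.

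The percentages assume 29 completers and full response; the longest recall assumes three gaps of 31 days. Which reading was meant cannot be determined from the Protocol. The affected outcome is secondary; the primary outcome and the sample size do not depend on it.

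**What to change.** Reconcile Outcomes, Subjective Analyses, Adverse events and Table 2. If reports by meal are wanted:

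- **Subjective Analyses:** replace the timing sentence with, for example, *A link to a short survey on adverse reactions since the test meal will be emailed on the day after each of the four test meals.*
- **Adverse events:** refer to *the survey sent the day after each test meal*.
- **Table 2:** add a row *Adverse reactions*, with the footnote *day after every test meal*.
- **Meal guess:** the same timing sentence governs it, so state whether it is asked after each meal or only after the last.

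If a single end-of-trial survey is intended, say so, have it ask about each of the four visits by date, and state in Outcomes that the between-meal comparison rests on recall.

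The cost of the first option is three more short emailed surveys per man, 3 × 29 = 87 in total, with some added burden and possible missed replies. No visits, samples or blood draws are added. If surveys after each meal were already planned, the change is wording only.
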